## **STATISTICAL ANALYSIS PLAN**

### **RANDOMIZATION**

Subjects who meet all inclusion and exclusion criteria will be randomized into two groups, glutamine and control group. Subject allocation will be carried out through block randomization and known only by the pharmacist, and the confidentiality are maintained so that subjects, doctors/nurses, researchers, and data analysers does not know the allocation of each subject.

### **SAMPLE SIZE JUSTIFICATION**

#### **Sample size calculations**

The sample size of this study is obtained from the two-way hypothesis testing formula for the two mean values in two independent groups with a confidence index ( $\alpha$ ) of 95% and power of 80%. Results are considered statistically significant if  $p < 0.05$ . The details of the estimated size of the research subject are as follows:

$$n_1 = n_2 = 2 \left[ \frac{(Z_\alpha + Z_\beta)s}{(X_1 - X_2)} \right]^2 = 2 \left[ \frac{(1.96 + 0.84) 0.04}{(0.032)} \right]^2$$

$$n_1 = n_2 = 24.5 \text{ subjects} \rightarrow 25 \text{ subjects per group}$$

Legend:

$n_1$  : Number of subjects in the intervention group (glutamine group)

$n_2$  : Number of subjects in the control group

$s$  : Standard deviation = 0.0415

$Z_\alpha$  : Z value in 95% confidence index = 1.96

$Z_\beta$  : Z value of test power = 0.84

$X_1 - X_2$  : Difference in mean value = 0.032

Assuming a 20% drop out event, the final sample size are:

$$n = 50 + (50 * 20\%)$$

$$n = 50 + 10$$

$$n = 60 \text{ subjects}$$

For a fixed sample size design, the sample size required to achieve a power of  $1-\beta=0.84$  for a two sided t-test at level  $\alpha=0.05$  under these assumptions amounts to a total of 60 patients, or 30 patients in each treatment group.

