#### *Data Collection*

Data on sex, age, weight, height and preoperative EF are collected through direct history-taking and preoperative medical records. Data on CPB time, aortic cross-clamping time, number of distal coronary artery grafts are collected from surgery reports. Arterial blood sampling for troponin I levels measurement are collected: (1) before induction, (2) at 5 minutes, (3) at 6 hours, (4) at 24 hours, and (5) at 48 hours after CPB. Plasma troponin I is measured using the troponin I (human) ELISA kit (Abnova, KA0233) with colorimetry method. Arterial blood samples for plasma glutamine levels measurement are collected before induction and 24 hours after the CPB. Plasma glutamine levels is measured using the Sigma–Aldrich GLN1 glutamine/glutamate determination kit (Sigma–Aldrich, GLN1-1KT) using colorimetry method. To obtain plasma samples, blood is centrifuged for 15 minutes at a speed of 3500 X G within a maximum period of 30 minutes after collection and is stored at -80°C.

A 5×5 mm sample of the right atrial appendage tissue are collected at 5 minutes after CPB and are immediately transported to the laboratory at 4°C within 30 minutes of collection. The tissue sample is divided for  $\alpha$ -ketoglutarate ( $\alpha$ -KG) measurement and paraffin block preparation for histopathological examinations. A total of 20 mg of tissue is homogenized and centrifuged to obtain the supernatant. A protease inhibitor is added to the supernatant and then stored at -80°C until cellular  $\alpha$ -KG levels are examined. The examination of  $\alpha$ -KG is performed using  $\alpha$ -KG assay kit (Abcam, ab83431) with colorimetry method.

Myocardial injury score is measured on preparations stained with hematoxylin and eosin (H&E) with a scoring system from 0 to 3 as follows: 0 = no change; 1 = slight changes: focal myocyte damage or small multifocal degeneration with slight degree of inflammation; 2 = moderate changes: extensive myofibrillar degeneration and/or diffuse inflammatory process; 3 = severe changes: necrosis with diffuse inflammatory process. Terminal deoxynucleotidyl transferase-mediated deoxyuridine triphosphate nick end-labelling (TUNEL) staining is performed using the TUNEL assay kit (Abcam, ab206386). Cell nuclei with positive TUNEL staining is colored brown. The apoptotic

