index is calculated based on the average number of cells with positive TUNEL staining. Expression of anti-cardiac troponin I is observed using anti-cardiac troponin I antibody (Abcam, ab47003). Measurement of anti-cardiac troponin I expression is performed on preparations stained with anti-cardiac troponin I antibody using a scoring system ranging from 0 to -3, as follows: 0 = no loss of staining; -1 = minimal decrease in staining, compared to normally stained tissue; -2 = clear decrease in staining with some positivity (brown color) remaining; -3 = no positive (brown color) staining. For quantitative analysis, histopathological examinations are made on as many as six fields of view per specimen under a light microscope (Olympus BX50, Tokyo, Japan) and photographed for further analysis. The histopathological specimens are assessed separately by two blinded examiners to get an average score.

Arterial blood samples for plasma lactate levels measurement are collected: (1) before induction, (2) at 5 minutes, (3) at 6 hours, (4) at 24 hours, and (5) at 48 hours after CPB. Lactate examination is performed using the Nova Biomedical Stat Profile® pHOX Ultra analyzer (Nova Biomedical, Waltham, MA, USA) with basic enzymatic method.

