Ejection fraction measurements are taken: (1) after induction and (2) at 5 minutes after CPB, through TEE examination using the modified Simpson method. Cardiac index (CI) measurements are taken: (1) after induction, (2) at 5 minutes, (3) at 2 hours, (4) at 6 hours, and (5) at 24 hours after CPB. The values are obtained from calculating cardiac output (CO) per body surface area (in m^2). Cardiac output is measured via a pulmonary artery catheter using thermodilution method. The measurements are performed three times, averaged, and considered valid if the variation between the three values is less than 10%. Body surface area is calculated using the Mosteller formula. Morbidity variables consist of ventilator time, postoperative use of vasoactive and inotropic agents, and duration of intensive care are collected from the medical record. Vasoactive and inotropic score (VIS) is calculated (VIS = dopamine dose [μg kg min] + dobutamine [μg kg min] + 100 × epinephrine dose [μg kg min] + 10,000 × vasopressin [units kg min] + 100 × norepinephrine dose [μg kg min]) using the maximum dosing rates of vasoactive and inotropic medications (μg kg min or IU kg min) during the first 24 hours after postoperative ICU admission.

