**Methods of Intervention:**

Subjects eligible for the study will review and undergo informed consent. Once consented, subjects will be randomly assigned to undergo:

- Glutamine Group, blind: will receive intravenous infusion of 0.5 mg/kgbw L-alanyl-L-glutamine dipeptide (Dipeptiven, Fresenius Kabi, Bad Homburg, Germany) diluted in normal saline up to 500 mL, started after induction of anesthesia for 24 hours
- Control Group, blind: will receive intravenous infusion of 500 mL normal saline, started after induction of anesthesia for 24 hours

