#### Primary Endpoint

Plasma glutamine before induction to anesthesia and 24 hours after CPB, and plasma troponin I before induction to anesthesia, 5 minutes, 6 hours, 24 hours and 48 hours after CPB.

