### Cardiac Index and Ejection Fraction Measurement

Parameters	Pre-operation	Time after CPB				
		5 minutes	30 minutes	2 hours	6 hours	24 hours
Cardiac Index	1: 2: 3:	1: 2: 3:	1: 2: 3:	1: 2: 3:	1: 2: 3:	1: 2: 3:
Ejection Fraction (EF)						
Echocardiography Operator	EF 1:  dr. _____  —  EF 2:  dr. _____  —					

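### No primary analysis model is stated; prespecifying adjustment for the pre-induction values already scheduled is a near-costless gain

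*Combined protocol and SAP*

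**What the plan says.** The part headed Statistical Analysis Plan covers randomization, sample size, and the primary and secondary endpoint lists, then moves on to safety and data monitoring. It gives no analysis model, covariate, summary measure, repeated-measures method or multiplicity rule.

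The only inferential content is under Sample size calculations: a "two-way hypothesis testing formula for the two mean values in two independent groups", a significance threshold of p < 0.05, and a two-sided t-test for 30 per group.

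The primary endpoint has two markers. For glutamine, Data Collection states: "Arterial blood samples for plasma glutamine levels measurement are collected before induction and 24 hours after the CPB". For troponin I, the Primary Endpoint section lists "plasma troponin I before induction to anesthesia, 5 minutes, 6 hours, 24 hours and 48 hours after CPB". Each marker therefore has one value from before the infusion, which is "started after induction of anesthesia for 24 hours". Glutamine has one later value and troponin I has four.

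**The concern.** A pre-induction value cannot respond to an infusion that starts after induction, so its natural role is as a baseline. The plan does not say whether the comparison is of raw follow-up values, of change from baseline, of follow-up adjusted for baseline, or of a trajectory over time. It also does not say which troponin time carries the test.

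Two things follow.

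- **Prespecification.** The primary endpoint holds five post-baseline comparisons (one glutamine, four troponin I). Each is open to several treatments of baseline, under a single 5% threshold. These choices remain open until the data are seen.
- **Precision.** If the sample-size test became the analysis, information from samples already scheduled would be discarded. Adjusting for baseline multiplies the residual variance by 1 − r², where r is the correlation between baseline and follow-up.

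**Working it through.** **Inputs from the documents.** From Sample size calculations: two-sided 5% level ("Z value in 95% confidence index = 1.96"); Zβ 0.84; difference 0.032, with endpoint and unit not named; SD 0.04 in the formula but 0.0415 in its legend; 25 per group raised by 20% to 60 in total. From the section on handling withdrawals: discontinued subjects are not replaced. A 20% loss from 60 leaves 48, or 24 per arm.

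**Assumptions.** The SD is that of the follow-up value. The documents do not give r, so a range is shown.

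**Step 1: the plan's own figure.** 2 × [(1.96 + 0.84) × 0.04 / 0.032]² = 2 × 3.5² = 24.5, so 25 per arm, and 50 × 1.2 = 60. The stated number reproduces with SD 0.04. With the legend's 0.0415 the formula gives 26.4, so 27 per arm.

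**Step 2: unadjusted power.** Noncentral t, df = 2n − 2, noncentrality = 0.032 / (s√(2/n)).

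- n = 30: 0.861 (s = 0.04), 0.836 (s = 0.0415).
- n = 24: noncentrality is 0.032 / (0.04 × 0.2887) = 2.77, giving 0.774. For s = 0.0415 it is 2.67, giving 0.744.

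**Step 3: ANCOVA power at 24 per arm.** Residual SD = s√(1 − r²), df = 2n − 3 = 45. The first figure in each pair ignores the cost of estimating the baseline slope. The second multiplies the variance by 1 + 1/(2n − 4) = 1 + 1/44.

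| r | 1 − r² | s = 0.04 | s = 0.0415 |
|---|---|---|---|
| unadjusted | – | 0.774 | 0.744 |
| 0 | 1.00 | 0.774 / 0.765 | 0.743 / 0.734 |
| 0.2 | 0.96 | 0.790 / 0.781 | 0.760 / 0.751 |
| 0.3 | 0.91 | 0.811 / 0.803 | 0.782 / 0.773 |
| 0.5 | 0.75 | 0.879 / 0.872 | 0.855 / 0.847 |
| 0.7 | 0.51 | 0.967 / 0.964 | 0.955 / 0.951 |

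Simulation with 100,000 trials per r (n = 24, s = 0.0415) gave 0.736, 0.751, 0.774, 0.848 and 0.951 for r = 0, 0.2, 0.3, 0.5 and 0.7, in line with the second figures. Power reaches 80% at r of about 0.25 to 0.29 (s = 0.04) or 0.36 to 0.39 (s = 0.0415). Ignoring the slope cost, 24 per arm acts like 24/0.96 = 25 at r = 0.2 and 24/0.75 = 32 at r = 0.5.

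**Step 4: what leaving the choice open means.** A change-score t-test has variance factor 2(1 − r) if baseline and follow-up variances are equal. At 24 per arm and s = 0.04 its power is 0.573, 0.630, 0.774 and 0.938 at r = 0.2, 0.3, 0.5 and 0.7. At r = 0.3, therefore, three analyses that the plan permits have power of 0.63 (change), 0.77 (raw follow-up) and 0.80 (ANCOVA).

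**Step 5: the other reading of the SD.** If 0.04 or 0.0415 is the SD of change, ANCOVA has variance factor (1 + r)/2 relative to the change-score test. That test then has the unadjusted power of Step 2. At 24 per arm and s = 0.0415, with the slope cost, ANCOVA power is 0.916 at r = 0.2, 0.847 at 0.5, 0.800 at 0.7 and 0.778 at 0.8, against 0.744. The gain now shrinks as r rises, and the thresholds in Step 3 do not apply.

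**The case against.** The strongest reply is that two claims of different weight are joined. The missing model and missing troponin contrast are documented omissions. Baseline adjustment is an efficiency recommendation, and the power figures support only that half. The t-test is named to justify the sample size, which does not fix the analysis. Listing pre-induction values in the endpoint is equally compatible with change scores or repeated measures. This is fair: the plan is silent on adjustment and does not rule it out.

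The figures also rest on an unnamed endpoint, an unstated kind of SD and an unknown r, which may differ between the markers. At r = 0.2 the gain is only one or two points. They describe a single raw-scale ANCOVA, not a log-scale repeated-measures model for troponin I. With all 60 patients analysed, unadjusted power is already 0.84 to 0.86. The shortfall at 24 per arm comes from the dropout allowance and the SD discrepancy, which are separate matters. All of this stands as a limit on the size of the benefit.

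It does not remove the point. Under either reading of the SD, ANCOVA gains over the comparison to which that SD belongs for the nonzero correlations shown, and it loses about one point at most if r is zero. The need to name a model and a contrast does not depend on r. The log scale, the sharing of the 5% level and the timing of ejection fraction and cardiac index are side items that can be settled separately.

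**Conclusion.** The concern holds. The plan states no primary analysis model, no role for the pre-induction values and no primary troponin contrast. Its only named test is an unadjusted one given as the basis for the sample size. Nothing here biases a randomized comparison; the loss is in precision and in protection against choices made after seeing the data.

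How much adjustment gains depends on r and on the SD being that of the follow-up value, neither of which the documents settle. No single power figure should be quoted as the benefit. The conclusion that adjustment is worth prespecifying rests on its small worst-case cost, since the samples are already planned. The change should be made, but it is not a fatal defect.

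**What to change.** Add to the SAP, before unblinding:

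1. **Glutamine:** the 24-hour value compared between arms by ANCOVA with the pre-induction value as covariate.
2. **Troponin I:** one repeated-measures model (log scale suggested) with treatment, time, treatment-by-time and the pre-induction value, and one named time point or contrast as the primary test.
3. **Error rate:** how the two primary markers share the 5% level. Baseline adjustment does not address this.
4. **Lactate:** adjust for its pre-induction value, which is also scheduled ("Arterial blood samples for plasma lactate levels measurement are collected: (1) before induction").
5. **Ejection fraction and cardiac index:** first state the order of events. Data Collection says "Ejection fraction measurements are taken: (1) after induction and (2) at 5 minutes after CPB" and also puts the first cardiac index after induction. The infusion too is "started after induction of anesthesia for 24 hours", while the case report form labels the first column "Pre-operation". These passages must be reconciled; adjust only if the first measurement precedes the infusion.
6. **Sensitivity:** keep the unadjusted t-test.

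The cost is SAP wording and one degree of freedom per covariate. For the primary markers and lactate, no patient, sample or visit is added.

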**Handling of Participant Withdrawals or Termination:**

Although subjects may withdraw from the study at any time and for any reason, (or may be withdrawn at the investigator's discretion), subject withdrawal should be avoided as much as reasonably possible. In any case, appropriate follow-up for withdrawals or termination. Subjects who are discontinued are not to be replaced. For subjects considered discontinued, the CRF must be completed up to the last visit performed.

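### The sample size section contradicts itself (SD 0.04 or 0.0415, power 80% or 0.84), and 60 randomised less the planned 20% drop-out gives about 74–79% power

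*Combined protocol and SAP*

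**What the plan says.** All of the sizing is in the SAP under Sample size calculations.

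- The opening sets a confidence index "of 95% and power of 80" per cent, for a two-sided comparison of two independent means.
- The bracket of the formula contains "1.96 + 0.84) 0.04", that is, an SD of 0.04. The result is 24.5, rounded up to 25 per group.
- The legend defines the same symbol differently: "Standard deviation = 0.0415". It also gives "Difference in mean value = 0.032" and lists 0.84 as the Z value for power.
- The allowance for losses is introduced with "Assuming a 20% drop out event, the final sample size are" and computed as 50 plus 20% of 50, which is 60.
- The closing sentence says that, for a two-sided t-test, the size needed for a power of 0.84 "under these assumptions amounts to a total of 60 patients, or 30 patients in each treatment group".

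The protocol section Handling of Participant Withdrawals or Termination adds: "Subjects who are discontinued are not to be replaced". The Primary Endpoint section names two variables, beginning "Plasma glutamine before induction to anesthesia and 24 hours after CPB, and plasma troponin I before induction to anesthesia"; troponin I then continues at four further times after bypass.

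**The concern.** Four things do not fit together.

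1. One symbol has two SD values, and they give different answers from the same formula. No source is given for either.
2. Adding 20% of the evaluable number does not protect against a 20% loss of the randomised number.
3. Power is 80% at the start and 0.84 at the end. The second figure is tied to all 60 patients, although a 20% loss has just been assumed.
4. No variable, time point or unit is attached to the difference of 0.032 or to the SD. There are two primary variables, measured at two and at five times, so the stated power belongs to no identified comparison.

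At stake is how a null result would be read. A reader would take the risk of missing the stated difference to be 20% or 16%, when the plan's own assumptions imply more, and could not tell which endpoint that risk applied to.

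**Working it through.** **Inputs**, all from Sample size calculations: difference 0.032; SD 0.04 (formula) or 0.0415 (legend); two-sided alpha 0.05; equal groups; 20% drop-out; 60 randomised.

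**Plan's own figure.** n per group = 2 × [(1.96 + 0.84) × SD / 0.032]²

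- SD 0.04: 2 × (2.80 × 0.04 / 0.032)² = 2 × 3.5² = 24.5, so 25 per group and 50 in total. This reproduces the plan.
- SD 0.0415: 2 × (2.80 × 0.0415 / 0.032)² = 26.4, so 27 per group and 54 in total.

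**Drop-out.** The plan takes 50 × 1.20 = 60. But 60 × 0.80 = 48, or 24 per group, which is below the required 50. Inflating so that 80% of those randomised meet the requirement gives 50 / 0.80 = 62.5 (64 in equal groups) at SD 0.04 and 54 / 0.80 = 67.5 (68) at SD 0.0415.

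**Power.** Normal formula: Φ[(0.032 / SD) × √(n/2) − 1.96]. For 24 per group at SD 0.04: 0.8 × √12 − 1.96 = 0.811, and Φ(0.811) = 0.791. The t-test power uses the noncentral t distribution with 2n − 2 degrees of freedom and noncentrality (0.032 / SD) × √(n/2).

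| Evaluable per group | SD 0.04: normal | SD 0.04: t-test | SD 0.0415: normal | SD 0.0415: t-test |
|---|---|---|---|---|
| 24 (20% of 60 lost) | 79.1% | 77.4% | 76.2% | 74.4% |
| 25 (10 of 60 lost) | 80.7% | 79.2% | 77.8% | 76.2% |
| 30 (none lost) | 87.3% | 86.1% | 84.8% | 83.6% |

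**Where 0.84 comes from.** Thirty per group gives 0.836 by t-test, which rounds to 0.84, only with SD 0.0415 and no losses. The 25 per group comes only from SD 0.04. No single set of stated inputs yields both. The listed Z value is also 0.84, and Φ(0.84) = 0.7995, the 80% target; a slip from Z value to power is possible but cannot be shown from the text.

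**Losses that 60 patients can bear**, computed as 60 minus twice the group size needed:

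| Target | SD 0.04: normal | SD 0.04: t-test | SD 0.0415: normal | SD 0.0415: t-test |
|---|---|---|---|---|
| 80% | 10 (17%) | 8 (13%) | 6 (10%) | 4 (7%) |
| 0.84 to two decimals | 6 (10%) | 4 (7%) | 2 (3%) | 0 |

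Every entry is below the planned 20%, which is 12 patients.

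**Size for 80% after a 20% loss by t-test.** 26 per group: 52 / 0.80 = 65, so 66 in equal groups (SD 0.04). 28 per group: 56 / 0.80 = 70 (SD 0.0415).

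**The case against.** The plan never gives 48. Its own arithmetic is 50 plus 10, so it may have meant a loss of 10, leaving 25 per group. With its own formula and its formula SD, power is then 80.7% and the 80% target is met. Even at 24 per group that combination gives 79.1%, under one point short. The low end of 74.4% stacks three steps: the inflation (80.7% to 79.1%, 1.6 points), the legend SD (79.1% to 76.2%, about 3 points) and the t-test (76.2% to 74.4%, about 1.8 points). The 0.84 sentence is about right if all 60 are analysed at the legend SD, so 80% after losses and 0.84 at full enrolment need not conflict. Finally, no analysis set is defined, and the case report form is completed up to the last visit, so some dropped-out patients could contribute early values.

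Part of this stands. The shortfall is conditional on losing and excluding 12 of 60, and the unresolved SD contributes more to it than the inflation slip. But a loss of 10 is 16.7% of 60, not 20%, and it reaches 80% in only one of four variants and 0.84 in none. The closing sentence itself names a t-test, which gives 77.4% or 74.4%. Adding patients for drop-out, without replacement, makes sense only if dropped-out patients are not evaluable. None of this resolves the two SDs or supplies the missing endpoint.

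**Conclusion.** The point holds. The SD is inconsistent (25 or 27 per group), the inflation does not deliver the required number, and the two power figures do not rest on one set of assumptions. If 20% of 60 are lost and excluded, power is 77–79% at SD 0.04 and 74–76% at SD 0.0415. That is about 1 to 6 points below 80% and 5 to 10 below 0.84, with a type II error of about 21–26%. The gap to 80% is small in the most favourable variant; the gap to 0.84 is clear in all of them.

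These figures assume a true difference of 0.032, an SD that applies to the patients actually analysed, equal losses in the two groups and no contribution from dropped-out patients. They also inherit the plan's main gap: until the endpoint is named, they describe a comparison that nobody can identify. The fault should be fixed; it does not undermine the trial as a whole.

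**What to change.** Keep 60 and correct the text.

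- Reconcile the two SD values and cite the source. The documents do not show which is right.
- Name the primary variable, time point and unit to which 0.032 and the SD refer.
- Show the inflation as division by 0.80: 50 / 0.80 = 62.5 if the SD is 0.04, or 54 / 0.80 = 67.5 if it is 0.0415. State that 60 is below this.
- State that the power assumes dropped-out patients are not analysed.
- Replace the 0.84 sentence with the following, keeping only the figures for the reconciled SD:

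> With 60 randomised and 48 evaluable after 20% drop-out, the two-sided t-test has power of about 77% (SD 0.04) or 74% (SD 0.0415) to detect a difference of 0.032 in [endpoint, time point]. With no drop-out, the best case, it would be about 86% or 84%.

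This changes wording only and adds no patients. The price is a less favourable stated power, below 80%. If the sponsor prefers to hold 80% after a 20% loss, the trial needs 64 (plan's formula) or 66 (t-test) patients at SD 0.04, and 68 or 70 at SD 0.0415.
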